20 recommended the use of convalescent plasma collected from patients who had recovered from Ebola virus
21 as an empirical treatment during the outbreak⁸. In 2015, a protocol for the use of convalescent plasma was
22 utilized in the treatment of Middle East respiratory syndrome coronavirus⁶.

23
24 The outbreak of severe acute respiratory syndrome coronavirus 2 (SARS-CoV-2) was declared a
25 pandemic by WHO on 3/11/2020. On 3/27/20, there were almost 530,000 cases confirmed in the world,
26 with over 23,700 deaths in 202 countries affected⁹. According to WHO, management of COVID-19 has
27 mainly focused on infection prevention, case detection and monitoring, and supportive care⁹. However,
28 no specific anti-SARS-CoV-2 treatment is recommended because of the absence of evidence. During the
29 last week of March, the United States has reported more cases than any other country, thus becoming a
30 new epicenter of the disease. Due to the gravity and urgency of the COVID-19 pandemic, formal
31 multicenter clinical trials for feasibility and medical effectiveness for collection and use of convalescent
32 plasma are not immediately feasible¹⁰⁻¹¹.

33 Now we have validated FDA Emergency Use Authorization (EUA) approved serological assays to
34 specifically detect SARS-CoV-2 antibodies, however, the quantitative result is still in the investigational
35 state and quantification of neutralizing antibodies are not available, yet. Until it becomes available, IgG
36 Index may soon be more widely available and standardized.¹² We currently lack validated serological
37 assays to specifically detect SARS-CoV-2 antibodies, however, technology is rapidly evolving and
38 quantification of neutralizing antibodies may soon be more widely available and standardized¹². Even in
39 the absence of that technology in hand, convalescent plasma from recovered individuals may provide
40 therapeutic benefit nonetheless, as neutralizing antibodies will inevitably be present in plasma. Indeed,
41 there are a few centers around the world with investigational protocols for convalescent plasma infusion
42 as a treatment for COVID-19 at the present time¹³⁻¹⁵. Therefore, under close supervision by the Food and
43 Drug Administration (FDA) in the context of an Investigational New Drug application (IND) pathway¹⁶,
44 the collection and investigational use of convalescent plasma in accordance with the safety and quality

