4 will be performed to permit retrospective determination of the characteristics of an effective product and
5 dosage regimen, and the characteristics of patients most likely to benefit¹⁸.

6 Data and blood specimen will be banked for future use pursuant to the IRB Approved Inova COVID-19
7 Biobanking Protocol. We will follow the guidelines and procedures for specimen storage and access as
8 described in the IRB approved Inova COVID-19 Biobanking Protocol.

9 Specimens will be stored at the Office of Research at Inova Biobank with standard certifications in place.

10

1 **PLASMA RECIPIENTS:**

2 **Inclusion Criteria for Recipients of COVID-19 Convalescent Plasma:**

3 Patients in the Inova Health System with confirmed COVID-19 by PCR testing

4 Age \geq 13 years

5 Currently hospitalized with COVID-19 infection with severe or life-threatening clinical syndrome²² as
6 follows:

7 Severe COVID-19: (three or more of the following)

8

- 10 • Dyspnea
- 11 • Respiratory rate \geq 30/min
- 12 • Blood oxygen saturation (SpO₂) \leq 94% on room air
- 13 • Partial pressure of arterial oxygen to fraction of inspired oxygen (P:F) ratio $<$ 300
- 14 • Pulmonary infiltrates $>$ 50% of lung parenchyma within 24 to 48 hours

15 Life-threatening disease is defined as: (one of the following)

- 16 • Respiratory failure
- 17 • Septic shock, and/or
- 18 • Multiple organ dysfunction or failure

19 Patient must provide informed consent or have health care power of attorney/next of kin provide consent
20 if he/she cannot.

21 **Exclusion Criteria:**

22 Contraindication to receive plasma as deemed by the treating physician

23 Severe hypercoagulable state (documented in medical chart or by treating physician assessment)

24 Absolute IgA deficiency

25 Prior history of Transfusion Related Acute Lung Injury (TRALI)

26 Inability to tolerate plasma volume due to severe systolic or diastolic heart failure despite slower infusion
27 and diuretic administration

28 Positive pregnancy test (HCG)

29 **Recipient Screening Labs**

30 Blood Type

31 Total immunoglobulin (Ig) levels: IgG, IgA, IgM

32 Coagulation tests to include PT/INR and PTT

33 Complete blood count and differential

34 **Pre-Treatment Testing:**

35 Optional Blood draw for Inova COVID-19 Biobank (up to four tubes each) prior to each dose of plasma

36 **Target Recipient Recruitment:** 150-200 individuals

37 **Primary Endpoints:**

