38 1) Change in clinical status as captured by 7-point ordinal scale score (being utilized in Gilead Sciences
39 remdesivir trial^{19, 20}) at time of plasma infusion (day 0) compared to day 7:

40

- 44 1. Death
- 45 2. Hospitalized, requiring mechanical ventilation or ECMO

- 1 3. Hospitalized, requiring non-invasive ventilation or high flow oxygen
- 2 4. Hospitalized, requiring supplemental oxygen
- 3 5. Hospitalized, not requiring supplemental oxygen--requiring ongoing medical care
- 4 (COVID-19 related or otherwise)
- 5 6. Hospitalized, not requiring supplemental oxygen-not requiring ongoing medical care
- 6 (COVID-19 related or otherwise).
- 7 7. Not Hospitalized

8 2) Adverse events related to plasma infusion (within 6 hours of infusion) to include²³:

- 9 a) Transfusion-related events
 - 10 i. Transfusion Associated Circulatory Overload
 - 11 ii. Transfusion-Related Lung Injury
 - 12 iii. Allergic Reaction/Anaphylaxis
 - 13 iv. Transmission of transfusion transmitted diseases
 - 14 v. Febrile Transfusion Non-hemolytic Transfusion Reaction

15 Secondary Endpoints:

- 16 3) Change in 7-point ordinal scale score (being utilized in Gilead Sciences remdesivir trial) from time
- 17 of plasma infusion (day 0-prior to first infusion) to days 14, 21, and 28^{19,20}.
- 18 4) SOFA score at days 0, 7, 14, 21, 28²¹
- 19 5) Time to discontinuation of supplemental oxygen
- 20 6) Duration of hospitalization
- 21 7) Time to liberation from mechanical ventilation (for patients on a ventilator)
- 22 8) Need for mechanical ventilation (For those not on the ventilator)
- 23 9) All-cause Mortality [at 28 days]

24 ○

| Organ System, Measurement | SOFA Score | | | | |
|--|------------|-------------------|--|--|---|
| | 0 | 1 | 2 | 3 | 4 |
| Respiration PaO ₂ /FiO ₂ , mmHg | Normal | <400 | <300 | <200 (with respiratory support) | <100 (with respiratory support) |
| Coagulation Platelets x10 ³ /mm ³ | Normal | <150 | <100 | <50 | <20 |
| Liver Bilirubin, mg/dL (μmol/l) | Normal | 1.2-1.9 (20-32) | 2.0-5.9 (33-101) | 6.0-11.9 (102-204) | >12.0 (<204) |
| Cardiovascular Hypotension | Normal | MAP<70 mmHg | Dopamine ≤5 or dobutamine (any dose)** | Dopamine >5 or epinephrine ≤0.1 or norepinephrine ≤0.1 | Dopamine >15 or epinephrine >0.1 or norepinephrine >0.1 |
| Central Nervous System Glasgow Coma Score | Normal | 13-14 | 10-12 | 6-9 | <6 |

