21 transformations explored as needed. All analyses will be conducted using SAS (version 9.4, Cary, NC)
22 with p<0.05, two-tailed considered statistically significant.

23
24 Primary efficacy endpoints:

25 1. Gilead 7-point scale – For each time point (day 0 vs. 7), summary clinical status scores will be
26 calculated. Changes in scores will be subsequently assessed via a generalized linear mixed model
27 with clinical status assessed at day 0 vs. 7. A statistically significant increase of ± 2 points in β
28 from day 0 to day 7 will be considered as evidence of efficacy. A mixed model allows for
29 examination and inclusion of the variance-covariance matrix into the model as a result of expected
30 within-subject serial correlation as a result of repeated assessments over time.
31 2. Plasma transfusion related adverse events will be scored as 1+ vs. 0 and will be assessed via Chi-
32 Square test with a hypothesized distribution of expected AE (using the higher incidence estimate):
33 i. Transfusion Associated Circulatory Overload: 1:1,566 to 1:68 plasma units
34 transfused
35 ii. Transfusion-Related Lung Injury: 1:1,200 to 1:190,000
36 iii. Allergic Reaction/Anaphylaxis: 1-3%
37 iv. Febrile Transfusion Non-hemolytic Transfusion Reaction: 0.1-1%

38
39 Secondary endpoints:

40 1. Change in 7-point ordinal scale score and SOFA score over time will be assessed via individual
41 growth models (IGM). Times will be day0, 14, 21, and 28
42 2. Mortality will be assessed via Chi-Square test with a hypothesized current mortality rate of 1-5%
43 (age adjusted).
44 3. Need for mechanical ventilation for those not ventilator at time of plasma infusion will be
45 assessed via Chi-Square test with a currently available published estimates.

1 4. Time to discontinuation of supplemental oxygen, time to liberation from mechanical ventilation,
2 duration of hospitalization will be summarized as median (IQR) or rates and compared to currently
3 available published estimates.
4
5

6 **ADVERSE EVENTS AND TOXICITY MANAGEMENT**

7 **Definitions of Adverse Events and Serious Adverse Events**

9 **Adverse Events (AE)**

10 An AE is any untoward medical occurrence in a clinical study subject administered an investigational
11 product, which does not necessarily have a causal relationship with the treatment. An AE can therefore be
12 any unfavorable and/or unintended sign, symptom, or disease temporally associated with the use of an

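### 28-day mortality in severe or life-threatening inpatients is tested against an unsourced 1-5% range, with no rule for choosing the null and no severity matching

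*Combined protocol and SAP*

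**What the plan says.** The endpoint is "All-cause Mortality [at 28 days"], item 9 under Secondary Endpoints. In the Statistical Plan, Secondary endpoints, item 2, the analysis is: "Mortality will be assessed via Chi-Square test with a hypothesized current mortality rate of 1-5" per cent, followed by a parenthesis saying the rate is age adjusted. No citation, age bands, age-specific rates or method are attached.

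The general rule for all analyses is "p<0.05, two-tailed considered statistically significant".

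The adverse-event test in the same plan also starts from published ranges, but it states which end to use: "Square test with a hypothesized distribution of expected AE (using the higher incidence estimate"). Mortality has no such rule.

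Recipients must be "Currently hospitalized with COVID-19 infection with severe or life-threatening clinical syndrome" (Inclusion Criteria for Recipients). The recruitment target is "150-200 individuals". The study is open-label and no control arm is described.

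**The concern.** A one-sample test compares the observed death rate with a fixed number, so its meaning rests entirely on that number. Here the number is a fivefold range, and nothing shows that it describes patients as ill as those enrolled. Two problems follow.

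- **The result can depend on an unfixed choice.** If the null is settled after the deaths are known, the choice of end can decide whether mortality is called significantly high, significantly low or neither.
- **Case mix can look like harm.** If eligible patients have an underlying mortality above the null, a significant excess reflects how ill they were at entry. A therapy that lowered mortality could then be reported as significantly worse than expected.

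The Study Background gives one set of counts: "On 3/27/20, there were almost 530,000 cases confirmed in the world", "with over 23,700 deaths in 202 countries affected". Their ratio, 23,700/530,000 = 4.5%, lies inside the range. The plan does not say that 1-5% came from these counts. If it did, it would be a rate for all confirmed cases, not for severe inpatients.

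**Working it through.** The plan gives no power, critical value or sample-size derivation for mortality, so there is no stated figure to reproduce.

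**Inputs.** n = 150 and 200 (Target Recipient Recruitment); null p0 = 1% and 5% (ends of the stated range), plus 3% as a single age-adjusted value inside it; two-sided alpha 0.05.

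**Test.** For x deaths, chi-square = (x − n·p0)² / [n·p0·(1 − p0)], significant if above 3.84.

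**Step 1: cut-offs.**

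- p0 = 1%, n = 150: expected 1.5. x = 4 gives 2.5²/1.485 = 4.21, significant; x = 3 gives 1.52, not. x = 0 also gives 1.52 (p = 0.22).
- p0 = 1%, n = 200: expected 2.0. x = 5 gives 3²/1.98 = 4.55, significant; x = 0 gives 2.02 (p = 0.16).
- p0 = 5%, n = 150: expected 7.5. x = 13 and x = 2 both give 5.5²/7.125 = 4.25, significant; x = 12 and x = 3 give 2.84, not.
- p0 = 5%, n = 200: expected 10. x = 17 and x = 3 both give 7²/9.5 = 5.16, significant; x = 16 and x = 4 give 3.79, not.

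| Null | Excess at or above (n = 150/200) | Benefit at or below (n = 150/200) |
|---|---|---|
| 1% | 4 / 5 | none possible |
| 3% | 9 / 11 | 0 / 1 |
| 5% | 13 / 17 | 2 / 3 |

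**Step 2: does the choice of end matter?** The two ends disagree for every count from 0 to 12 of 150 except 3, and from 0 to 16 of 200 except 4. For example, 6/200 gives 4²/1.98 = 8.08 (p = 0.0045, excess) against 1% and 4²/9.5 = 1.68 (p = 0.19) against 5%. No count is significant in opposite directions at the two ends.

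**Step 3: chance of a significant excess.** This is the exact binomial probability of reaching the excess cut-off, P(X ≥ c | n, true rate). The true on-plasma rates are assumptions, because the documents give none for these patients.

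| Assumed on-plasma mortality | Null 5% (n = 150/200) | Null 3% (n = 150/200) |
|---|---|---|
| 5% | 0.039 / 0.024 | 0.336 / 0.417 |
| 7.5% | 0.336 / 0.332 | 0.800 / 0.891 |
| 10% | 0.746 / 0.793 | 0.969 / 0.992 |
| 12% | 0.922 / 0.954 | not tabulated |
| 15% | 0.993 / 0.998 | not tabulated |

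Against 1%, a true 5% gives 0.945 / 0.974. The excess cut-off never falls as p0 rises from 1% to 5%, so 5% is the most lenient reading.

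**Step 4: can a beneficial therapy be called worse?**

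- *Inside the plan's own range.* Suppose plasma lowers mortality from 5% to 3%. Tested against 1%, P(X ≥ 4 | 150, 3%) = 0.66 and P(X ≥ 5 | 200, 3%) = 0.72. With an exact test the figures are 0.47 and 0.56.
- *Against 5%.* The Study Background cites an odds ratio of 0.20 (95% CI 0.06-0.69) for mortality in H1N1. On-plasma rate = OR·odds / (1 + OR·odds). Assumed untreated mortality of 20%, 30% and 40% gives 0.05/1.05 = 4.8%, 0.0857/1.0857 = 7.9% and 0.1333/1.1333 = 11.8%. The chance of significant excess is then 2-3%, 41% and 91-94%, despite the benefit. These figures use the point estimate only. At 30% untreated, the limits of the interval give on-plasma rates of 2.5% and 22.8%, so the chance runs from almost nil to almost certain.

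**The case against.** The strongest reply has four parts.

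- **The range is not shown to be wrong.** The plan does not say which population 1-5% describes, and the documents contain no mortality rate for severe inpatients. This stands: the supportable statement is that the rate is not shown to be matched, and the reversal is conditional. Against 5% it needs on-plasma mortality above 5%, and becomes likely only above about 8.5%.
- **Age adjustment may yield one expected count.** If the rate varies by age across 1-5%, nobody chooses an end and the disagreement in step 2 falls away. That reading is possible, but no method is given. It also leaves severity untouched: a single expected rate of 3% gives significant excess in 97-99% of trials if true mortality is 10%.
- **The boundaries are test-specific.** With 1.5-2.0 expected deaths under 1%, the chi-square approximation is poor. An exact test moves the excess cut-offs from 4/5 to 5/6, and from 13 to 14 at 5% with n = 150. A shift of at most one death does not alter the conclusion.
- **It is secondary, and the raw rate will be seen anyway.** The plan ties evidence of efficacy only to the ordinal scale, and already describes death by frequency and percent. This limits the harm but does not make the p-value interpretable.

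**Conclusion.** The concern holds. The plan tests mortality two-tailed against an uncited range, with no selection rule, an undefined age adjustment and no severity matching. That much rests on the text alone. The size is also clear on the plan's own figures: the excess threshold moves from 4/5 to 13/17 deaths between the ends of the range, and at the 1% end benefit cannot be shown at all.

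That a beneficial therapy could be called worse is a conditional finding. It follows inside the range if the null is 1%. At the 5% null it depends on an assumed on-plasma mortality, with 33-34% of trials affected at 7.5%, 75-79% at 10% and over 99% at 15%. At 5% or below the chance is at most about 4%.

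This should be fixed, but it is not critical: the endpoint is secondary and no stopping or decision rule uses the test.

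**What to change.** Delete the chi-square test against 1-5%. Report 28-day all-cause mortality as deaths/n with an exact (Clopper-Pearson) 95% confidence interval. For example, 15/150 gives 10.0% (5.7-16.0%) and 20/200 gives 10.0% (6.2-15.0%).

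If a comparison is kept, prespecify one sourced reference rate matched on severity and age, state the adjustment method, report observed/expected deaths with an exact confidence interval, and label it non-randomised context, not evidence of a plasma effect. A concurrent untreated comparator is not needed for this fix. If one were added, it would first need an index-date rule to avoid immortal-time bias.

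The cost is a change of SAP wording and the loss of a mortality p-value. No new data are needed, since deaths are already to be described by frequency and percent. The optional comparison costs more, because a suitable severity-matched reference may not exist. Items 3 and 4 of the same list also lean on unspecified published estimates and could be reviewed at the same time.

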45 criteria of established regulatory standards is proposed for Inova Health Systems.

1 **Safety Considerations:**

2 1) Clinical use of convalescent plasma in this setting is regarded as investigational
3 as the safety and efficacy of convalescent plasma are unproven in the setting of this novel
4 pandemic. Collection and clinical use of this product will be managed as an experimental therapy
5 consistent with ethical safeguards (informed consent of donors and recipients, FDA approval
6 through IND pathway, institutional approval, and special labeling).

7 2) Procedures will maximize safety of both plasma donors and recipients.

8 a. Standard blood donation protocols and screening will be followed (Donor History
9 Questionnaire, Appendix E)

10 b. Potential donors will be assessed by physician or nurse practitioner to assure clinical
11 stability and full recovery (confirmed by nucleic acid amplification technology (NAT))
12 prior to donation

13 c. Plasma collections must be separated by \geq 28 days, eligibility must be re-evaluated at each
14 collection, and total volume collected will be based on estimated donor blood volume in
15 accordance to guidelines for healthy donors

16 d. As with other plasma therapies, ABO compatibility will be assured

17

18

19 e. Potential risks to convalescent plasma recipients will be discussed in the informed consent
20 process and monitored for closely in the hospital setting:

21 i. risk of unintended transmission of relevant transfusion transmitted diseases from
22 donor

23 ii. risks of transfusion related reactions

24 iii. theoretical risk of immune enhancement due to transferred antibodies that could
25 exacerbate the disease

26

27

28

29

30

31

32

33

34

35

36

37

1 Plasma Collection and Storage: Collection, storage, and preparation of plasma will be performed by the
2 Inova Blood Center Staff. The plasma product is to be handled like a regular or licensed FFP/FP24, with
3 special labeling. Convalescent plasma will be stored at the Inova Blood Donor Services Facility, the
4 largest hospital based donor center in the country. It is a well-established and regulated BSL2 facility
5 which is CLIA/CAP certified in full compliance with regulatory guidelines including AABB, FDA, with
6 use of good manufacturing practices.

7 The Inova Blood Center Staff are routinely engaged in automated plasma collection and preparation in

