- 26 • If donors have documentation of a repeat SARS-CoV-2 NAT nasopharyngeal test
27 from an outside source that is negative, this test result will be accepted in lieu of
28 repeating the SARS-CoV-2 NAT nasopharyngeal test at screening visit
- 29 • If phlebotomy is feasible and safe:
 - 30 ◦ Blood draw of two tubes (1 serum and 1 EDTA) of blood for SARS-CoV-2
31 antibody testing
 - 32 ◦ Blood draw of up to four additional tubes for COVID-19 Inova Biobank
33 specimen (optional) In cases of extreme urgency for recipient plasma
34 infusion, there may be an option of drawing an additional four tubes for
35 transfusion transmissible disease testing at screening visit to expedite
36 readiness of plasma for use (normally this blood is drawn at time of plasma
37 donation and may take an additional 1-2 days)

38 *If SARS-CoV-2 NAT nasopharyngeal test is positive at screening visit, potential donor will not
39 be allowed to donate plasma and will be given the option to return for a repeat screening SARS-
40 CoV-2 NAT nasopharyngeal test after 7 or more days.

- 41 • Once a negative SARS-CoV-2 NAT nasopharyngeal test has been confirmed,
42 plasma donation appointment can be scheduled

1 ** If timely antibody testing should become available at a future date that allows prospective
2 evaluation of antibody profiles, donors may be asked to postpone plasma donation and return for
3 repeat antibody testing prior to donation in order to enhance the presence of IgG in the plasma.

4 *** If SARS-CoV-2 antibody testing becomes more standardized in the future, may be able to
5 forgo NAT nasal swab test if documented SARS-CoV-2 infection was >28 days prior to screening
6 visit.

7

8 3) Plasma Donation

9 • Location: Inova Blood Donor Services Facility May occur same day as screening visit after
10 confirmed negative NAT test result, or on a subsequent day.

11 • Completion of donor history questionnaire (in accordance to standard practice for blood
12 donation). Plasma collection performed by blood donor services staff member according to
13 standard protocol using automated apheresis machine (TRIMA by Terumo-BCT))

14 • Plasma is collected in an aseptic manner into a closed sterile system

15 • Duration of procedure is approximately 1.5 hours

16 • Total collection volume dependent on individual donor characteristics and includes:

17

18 o Whole blood sample collected into the sample diversion pouch and aliquoted into:

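### The need-for-ventilation test counts only patients still unventilated at infusion and compares them with outside rates of unstated time origin; recipients should also be counted from consent

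*Combined protocol and SAP*

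**What the plan says.** **Ventilation.** Statistical Plan, Secondary endpoints, item 3 reads "Need for mechanical ventilation for those not ventilator at time of plasma infusion will be" "assessed via Chi-Square test with a currently available published estimates". It names no rate, source, population, starting point or horizon for the published figures.

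**Clock.** Primary Endpoints, item 1 measures status "at time of plasma infusion (day 0) compared to day 7". The Secondary Endpoints list measures the ordinal scale from the time "of plasma infusion (day 0-prior to first infusion) to days 14, 21, and 28". After discharge, contacts at days 7 to 28 are counted from the first dose (Post-Treatment Blood Draws).

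**Mortality.** Statistical Plan, Secondary endpoints, item 2: "Mortality will be assessed via Chi-Square test with a hypothesized current mortality rate of 1-5" per cent, age adjusted. The endpoint list sets the horizon at 28 days but not its start.

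**Analysis set.** None is defined. Nothing says how a patient who consents but is never infused is followed or counted.

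**Between consent and infusion.** No interval is stated.
- Some text points to possible delay. Safety Considerations, 2) d: "As with other plasma therapies, ABO compatibility will be assured". The donor schedule says blood for disease testing is ordinarily taken at plasma "donation and may take an additional 1-2 days". It offers earlier testing when a recipient's need is urgent. The blood bank may also try to meet requests from outside the trial.
- Other text limits it. Donors are enrolled first (Phase 1), plasma is frozen with a 365-day shelf-life, and trial recipients have priority for trial plasma.

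**The concern.** In a single-arm study, an outside rate is the only comparator for this endpoint. The treated series starts at infusion and keeps only those who reached it unventilated. If the published rate counts patients from admission or diagnosis, it includes early intubations that the treated series has dropped. Where risk is highest early, plasma can then look better with no effect.

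The entry criteria make early events plausible: rapidly progressing infiltrates, respiratory failure and septic shock are among the qualifying features. The comparison is tested at two-sided 0.05, so a mismatch in time origin can become a claim of benefit.

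**Working it through.** The plan gives no power or bias figure to reproduce. The check asks how far the infused-only rate can move with no plasma effect.

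**Inputs from the documents.** Two-sided 0.05; target of 150-200 recipients; chi-square test against a fixed rate; follow-up counted from the first dose.

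**Assumptions, not in the documents.** Wait w of 1-3 days. True 28-day ventilation risk of 30%, equal to the benchmark. Weibull time to intubation with shape k = 0.5 (strongly front-loaded), 0.7 (moderately) or 1.0 (constant hazard). The 28 days restart at infusion, as the follow-up schedule suggests.

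**Step 1: infused-only risk.** With S(t) = exp(-λt^k) and S(28) = 0.70, λ = 0.3567/28^k. The share intubated while waiting is 1 - S(w). Risk after infusion is 1 - S(w+28)/S(w). For k = 0.5 and w = 2:
- λ = 0.3567/5.292 = 0.0674
- S(2) = exp(-0.0674 × 1.414) = 0.909, so 9.1% leave
- S(30) = exp(-0.0674 × 5.477) = 0.691
- risk = 1 - 0.691/0.909 = 24.0%

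**Step 2: chance of a falsely better result.** With n = 200 and a benchmark of 30%, the standard error is √(0.30 × 0.70/200) = 0.0324. Significance needs a rate below 0.30 - 1.96 × 0.0324 = 0.2365, that is, 47 events or fewer. With n = 100 it needs 21 or fewer. Exact binomial probabilities for a 2-day wait:

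| Shape | Intubated while waiting | Infused-only risk | False 'better', n=200 | n=100 |
|---|---|---|---|---|
| 0.5 | 9.1% | 24.0% | 48% | 29% |
| 0.7 | 5.5% | 27.2% | 13% | 10% |
| 1.0 | 2.5% | 30.0% | 2.5% | 2.9% |

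For waits of 1 and 3 days at n = 200, shape 0.5 gives 28% and 63%, and shape 0.7 gives 8% and 19%. The 200 is an upper limit, because recipients already ventilated at infusion are not at risk.

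**Step 3: horizon.** If follow-up instead ended 28 days after consent, even a constant hazard would give (0.30 - 0.025)/(1 - 0.025) = 28.2%. Item 3 does not say which horizon applies.

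**Step 4: patients who improve.** Suppose 3% are intubated while waiting and a share g improves and is never infused. The infused-only rate is (0.30 - 0.03)/(1 - 0.03 - g): 27.8% for g = 0, 30.0% for g = 7%, and 31.0% for g = 10%. The bias disappears, then reverses.

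**Step 5: mortality as planned.** Against 5%, a significantly better result needs at most 2 deaths in 150 or 3 in 200. Against 1%, no result can be significantly better. If true mortality is 10-30% (assumed), dropping deaths during a 1-3 day wait still leaves 7.4-30%. The chance of looking better than 5% is then about 0.1% or less, and of looking worse 30-100%. The Study Background's all-case figures give 23,700/530,000 = 4.5%. This lies inside the 1-5% range, whereas recipients have severe or life-threatening disease.

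**Step 6: mortality with a matched rate.** If the benchmark were changed to fit severity, time origin would matter here too. With true and benchmark mortality of 20%, a 2-day wait, 200 patients and pre-infusion deaths uncounted, a falsely better result occurs 29% (shape 0.5) or 8% (shape 0.7) of the time.

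**The case against.** The strongest reply is that the wait may be short. Donors come first, units are frozen and stored, and trial recipients have priority. The 1-2 days of testing concern a newly donated unit, and they appear where the protocol offers a way to shorten them. Nothing shows that consent comes before a unit is allocated. This stands: the 2-day wait is an assumption.

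A constant hazard with the clock restarted at infusion gives no bias, and loss of improving patients can offset what bias there is. A published rate counted from treatment start in unventilated patients would also remove the mismatch. These points stand as well, so neither size nor direction is settled. But the plan names no such rate and collects nothing that would show which case applies.

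A reader might infer three stronger things that the documents do not support:
- **That plasma would look better on mortality.** A patient intubated while waiting stays in the mortality comparison if infused. The 1-5% reference appears too low for these recipients, so the net error most likely runs against plasma.
- **That pre-infusion deaths are excluded by rule.** The plan is silent; exclusion is only a likely consequence of starting at infusion.
- **That this is classical immortal-time bias.** No waiting time is credited to plasma. The problem is selection at entry against a benchmark whose own start is unknown.

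**Conclusion.** The point holds for need for mechanical ventilation. By the plan's own wording, patients intubated between consent and infusion leave the risk set, and the comparator's population and time origin are unstated. With a 2-day wait and a 30% risk, the infused-only rate falls by 0 to 6 percentage points depending on how front-loaded the risk is. The false-positive chance in plasma's favour runs from the nominal 2.5% to 48% at n = 200. These figures rest on assumed waits, risks and hazard shapes, and on no loss of improving patients.

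For mortality, the defect is only that the start of the 28 days and the analysis set are undefined. This is worth correcting in a secondary analysis that is tested for significance. It does not affect the primary endpoints' definitions.

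**What to change.** 1. Record for every recipient the consent date, the infusion date and, if never infused, the reason.
2. Follow all consented recipients by chart to day 28 for ventilation and vital status.
3. Report need for ventilation (among those not ventilated at consent) and 28-day mortality from consent, alongside the infused-only results from day 0. State the numbers who died, were intubated or improved while waiting.
4. For any test against an outside rate, name the rate's source, population and starting point, and use the version whose time origin and severity match it. Claim no benefit on ventilation if the two versions disagree.

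Counting from consent removes the selection whichever way it runs. It does not repair a benchmark of the wrong severity, which is why step 4 is needed. The cost is SAP wording, two dates and one reason field, and a little chart follow-up of patients never infused. Treatment does not change. The reported rates may be less favourable.
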